PROTOCOL

Title: Improving treatment personalization of pulmonary hypertension associated with diastolic heart failure

Protocol Version: 3
10/08/2018

Investigators:

[name], PhD, Assistant Professor
Department of Pharmacotherapy and Translational Research, UF

[name], Associate Professor
Division of Pulmonary, Critical Care and Sleep Medicine, UF

[name], Assistant Professor
Division of Pulmonary, Critical Care and Sleep Medicine, UF

Study Hypothesis and Specific Aims

The objective of this application is to evaluate nebivolol as a potential treatment for patients with pulmonary hypertension (PH) associated with diastolic heart failure, or heart failure with preserved ejection fraction (HFpEF). Our central hypothesis is that nebivolol improves PH severity in patients with HFpEF, as measured by hemodynamic and clinical parameters. The rationale for this research is that once we determine the extent to which nebivolol improves PH, it could be developed as a treatment for PH and HFpEF, especially if patients who respond best can be identified before treatment.

We will test our central hypothesis and accomplish these objectives by pursuing the following specific aim:

Define the clinical role of nebivolol as a potential treatment for PH associated with HFpEF using hemodynamic and functional status measurements.

Our working hypothesis is that nebivolol, via its β_1 -antagonistic and β_3 -agonistic activities, as well as its anti-inflammatory, anti-proliferative, and endothelial NO-stimulating properties, will decrease pulmonary pressures and improve 6-minute walk distance and dyspnea scores in patients with HFpEF-associated PH.

Background and Significance

Clinically, PH is marked by increased pulmonary vascular resistance leading to right heart failure, and ultimately death.¹ Thus, PH carries a poor prognosis, with a yearly mortality rate of 9%.² PH can include either pulmonary arterial hypertension (PAH) or pulmonary venous hypertension (PVH), which is often caused by left-sided heart failure. Increased pulmonary artery pressure (PAP) in patients with PVH develops from backward transmission of increased left atrial pressure, and is the most common cause of PH, with studies estimating its presence in 60-90% of heart failure patients.³⁻⁶ However, approximately half of these patients have PAPs that are disproportionately higher than expected from their left arterial pressure, with greatly increased peripheral vascular resistance.⁴ This increase in PAP is associated with significantly worse outcomes, with one study estimating that heart failure patients with very high PAP possess an increased the risk of death by greater than 2-fold compared to heart failure patients with normal PAP.⁷ Such poor outcomes are particularly troubling in patients with PH and HFpEF, where no established guidelines for treatment exist.⁸ Thus, development of treatments for this category of PH is greatly needed.

Current approved treatment classes for PAH, such as endothelin receptor antagonists and prostacyclins have either been shown ineffective, or have been associated with increased mortality when used in heart failure patients.^{9,10} Nebivolol is a third generation β -blocker which has been shown to improve diastolic dysfunction in both rats and humans with HFpEF.¹¹⁻¹³ In addition, this particular β -blocker has a profile that should make it ideal for treatment HFpEF patients with PH. Importantly, nebivolol has been shown in a clinical study to improve mean PAP and PCWP in HFpEF patients without PH.¹³ However, to what extent it improves these hemodynamic parameters in HFpEF patients, who also have PH, is unknown.

This project will contribute toward determining whether these potentially beneficial properties of nebivolol, known to improve diastolic dysfunction, will also improve PH severity in patients with HFpEF. This contribution will be important because it could uncover a potential treatment for a disease category that currently has no accepted treatments. If nebivolol significantly improves PH severity in patients with HFpEF, it can be further researched as a probable treatment. Furthermore, this project should also advance knowledge of the hemodynamic effects of chronic nebivolol treatment in HFpEF patients, as very few clinical studies have measured hemodynamics by right heart catheterization both before and after chronic oral treatment.

Methods

This project will be a prospective, open-label four-month clinical pilot study of 40 patients with PH and HFpEF. Patients will be started at 2.5 mg of nebivolol by mouth daily if they were not taking a beta-blocker at enrollment, and titrated up to 10 mg daily, as tolerated. Patients who cannot tolerate a dose increase will continue on the maximum tolerated dose throughout the study. Patients already on a beta-blocker at enrollment will begin on 5 mg and will be titrated to 10 mg daily. DNA and RNA will be collected for genomic studies of disease and drug response. All study procedures will occur at either the UF Clinical Research Center (CRC) or Shands Hospital.

Test/Procedure	Visit 1/1A (wk 0-1)	Call 1 (wk 1)	Call 2 (wk 2)	Visit 2 (wk 4)	Call 3 (wk 5)	Visit 3 (wk 8)	Call 4 (wk 9)	Visit 4 (wk 18)
right heart catheterization	X*							X
transthoracic echo	X*							X
electrocardiogram	X			X		X		X
6-minute walk distance	X			X		X		X
vital signs	X			X		X		X
dyspnea index	X			X		X		X
complete blood count	X			X		X		X
INR	X					X		X
liver function test	X			X		X		X
basic metabolic panel	X			X		X		X
nt-proBNP	X					X		X
RNA collection	X			X		X		X
DNA collection				X		X		
serum collection	X			X		X		X
change in nebivolol dose	X		X	X				X
adverse effect assessment		X	X		X		X	
medication history	X			X		X		X

* = if not done within previous 3 months as part of clinical care

Visit 1 (week 0):

- Blood sample: 2x 8 mL PAXgene (RNA), 1x 10mL lavender top (plasma and PBMCs), 1x 3mL lavender top (CBC with diff), 2x 4mL Li Heparin (nt-proBNP, CMP), 1x2.7mL blue top (INR)
- Vital signs: blood pressure, pulse, respirations, height, weight, etc.
- Dyspnea index
- 6-minute walk test
- Medication history
- EKG

- Patients will be asked to take oral nebivolol 2.5 mg (or 5 mg) once daily until Visit 2 (**if visit 1A is not needed**). Instruct patient to discontinue previous beta-blocker and begin nebivolol today if they have not taken any beta-blocker today, and tomorrow if they have already taken a beta-blocker today.
- Place note in medical record documenting name of study, responsible physician, procedures, and medication dose.
- If possible, schedule Visit 1A or Visit 2.
- Once complete, provide patient with compensation (\$50).

Visit 1A – IF NEEDED (week 0-1):

- If the patient has not received a two-dimensional transthoracic echocardiogram (TTE) within 3 months of enrollment, it will be done for research purposes, possibly on the same day as visit 1.
- If the patient has not received a right heart catheterization (RHC) within 3 months of enrollment, it will be done for research purposes (Appendix 1).
- Patients will be asked to take oral nebivolol 2.5 mg (or 5 mg) once daily until Visit 2. Instruct patient to discontinue previous beta-blocker and begin nebivolol today if they have not taken any beta-blocker today, and tomorrow if they have already taken a beta-blocker today.
- Once complete, provide patient with compensation (\$200).

Phone Call 1 (week 1):

- How does patient feel compared to before starting study drug?
- Any perceived side effects?
- If not done already, schedule Phone Call 2

Phone Call 2 – IF NEEDED (week 2):

- How does patient feel compared to before starting study drug?
- Any perceived side effects?
- If tolerated, increase nebivolol dose to 5 mg (after approval by study physician)
- If not done already, schedule Visit 2.

Visit 2 (week 4):

- Blood sample: 1x 6 mL purple top (DNA), 1x 8 mL PAXgene (RNA), 1x 10mL lavender top (plasma and PBMCs), 1x 3mL lavender top (CBC with diff), 1x 4mL Li Heparin (CMP)
- Vital signs: blood pressure, pulse, respirations, height, weight, etc.
- Dyspnea index
- 6-minute walk test
- Medication history
- EKG
- If tolerated, increase nebivolol dose to 10 mg once daily.
- Update medical record to reflect new dose.
- If possible, schedule Visit 3.
- Once complete, provide patient with compensation (\$40).

Phone Call 3 (week 5):

- How does patient feel compared to before starting study drug?
- Any perceived side effects?
- Provide results of safety assessment (everything looks similar to baseline OR significant difference in _____; the study physician recommends you _____.)

- If not done already, schedule Visit 3.

Visit 3 (week 8):

- Blood sample: 1x 6 mL purple top (DNA), 1x 8 mL PAXgene (RNA), 1x 10mL lavender top (plasma and PBMCs), 1x 3mL lavender top (CBC with diff), 2x 4mL Li Heparin (nt-proBNP, CMP), 1x2.7mL blue top (INR)
- Vital signs: blood pressure, pulse, respirations, height, weight, etc.
- Dyspnea index
- Medication history
- 6-minute walk test
- EKG
- If possible, schedule Visit 4.
- Once complete, provide patient with compensation (\$40).

Phone Call 4 (week 9):

- How does patient feel compared to before starting study drug?
- Any perceived side effects?
- Provide results of safety assessment (everything looks similar to baseline OR significant difference in _____; the study physician recommends you _____.)
- If not done already, schedule Visit 4.

Visit 4 (week 18):

- Blood sample: 2x 8 mL PAXgene (RNA), 1x 10mL lavender top (plasma and PBMCs), 1x 3mL lavender top (CBC with diff), 2x 4mL Li Heparin (nt-proBNP, CMP), 1x2.7mL blue top (INR)
- Vital signs: blood pressure, pulse, respirations, height, weight, etc.
- Dyspnea index
- Medication history
- 6-minute walk test
- EKG
- Two-dimensional transthoracic echocardiogram (TTE) for research purposes
- RHC for research purposes (Appendix 1).
- Based on study physician recommendation, patients will be advised on how to proceed with beta-blocker treatment after the end of the study.
- Update medical records to indicate patient has completed study.
- Once complete, provide patient with final compensation (\$250).

Eligibility Criteria

Study Population. This study will include PH patients from Shands Hospital and UF Health pulmonary hypertension and cardiology clinics. Patients must be diagnosed with PH by right heart catheterization (RHC). This procedure is the gold-standard for PH diagnosis and is the most accurate way to measure the hemodynamics necessary to differentiate subtypes of PH. Inclusion criteria for this study include:

1. Adults (≥ 18 years of age) with World Health Organization Group 2 Pulmonary Hypertension:
 - a. Mean pulmonary artery pressure (mPAP) ≥ 25 mmHg,
 - b. And pulmonary capillary wedge pressure (PCWP) ≥ 15 mmHg or left ventricular end diastolic pressure (LVEDP) ≥ 15 mmHg

2. Evidence of either diastolic dysfunction on echocardiogram OR elevated filling pressures on invasive hemodynamic testing OR BNP>200 (NT-proBNP>220) pg/mL
3. NYHA class II-IV symptoms
4. Left ventricular ejection fraction (LVEF) \geq 45%

To assure any effect on hemodynamics are not due to other medications, patients must have no changes within one month to their cardiovascular medication regimen, including ACE-inhibitors, angiotensin receptor blockers, diuretics, and nitrates. Exclusion criteria include:

1. Other causes of heart failure other than diastolic dysfunction, such as restrictive cardiomyopathy or infiltrative cardiomyopathy
2. Women who are pregnant or nursing
3. Liver cirrhosis,
4. primary valvular disease
5. Acute coronary syndrome
6. Causes of PH other than that of heart failure, such as: chronic thromboembolic PH, sickle-cell disease, or sarcoidosis
7. Severe bradycardia or greater than 1st degree heart block
8. Decompensated heart failure
9. Current use of a third generation beta-blocker (nebivolol, carvedilol, or labetalol) or high dose of other beta-blockers (greater than 100 mg daily of metoprolol, or equivalent).

Plans for subject selection, recruitment, and documentation of informed consent

This study will include PH patients from Shands Hospital and UF Health pulmonary hypertension and cardiology clinics. Eligibility will be reviewed and if requirements are met, patients will be approached to gauge interest. If interested, patients will be asked to provide informed written consent.

Description of Procedures

Hemodynamic Measurements. To confirm the diagnosis of PH associated with HFpEF and obtain baseline hemodynamic measurements, right heart catheterizations (RHCs) will be performed by UF cardiologists and pulmonologists using standard techniques. Any procedures done during catheterization beyond those mentioned will be at the discretion of the physician performing the for clinical indications.

Transthoracic echocardiograms (TTEs) performed by UF Health technicians will also be used to obtain further hemodynamic parameters, including those that are indicative of diastolic dysfunction. TTEs will be read by a cardiologist as per American Society of Echocardiography guidelines. Diastolic dysfunction will be determined by tissue Doppler imaging. RV measurements including size, lateral tricuspid annular velocity, E wave, A wave, and isovolumic relaxation time will be performed.

Functional Assessments. The 6-minute walk test will be performed in accordance with standard practice both at baseline and at completion of the study. Briefly, subjects will be asked to walk for six minutes along a pre-measured path, with a practice walk being performed first. Distance walked, oxygen saturation, and a Dyspnea Index will be determined.

Statistical Methods

Planned statistical analysis: Student's t-test for paired samples will be used to determine differences between hemodynamic measurements taken before and after six months of nebivolol
Personalized Treatment of PH with DD Protocol, Version 3, 10/08/18

treatment. Thus, each patient will serve as their own control. The two primary efficacy phenotypes to be measured are mPAP and PCWP. In secondary analyses, mitral valve Doppler flow velocity pattern, CO, PVR, CI and TPR will also be analyzed in an attempt to better characterize the mechanisms by which nebivolol affects the hemodynamic profile. In addition, Student's t-test for paired samples will be used to determine differences in 6-minute walk time before and after nebivolol treatment. Fisher's Exact Test will be used to compare dyspnea scores before and after six months of nebivolol treatment. In all analyses, $P \leq 0.05$ in a two-tailed distribution will be considered statistically significant. Statistical analyses will be performed using SAS 9.2 (SAS Institute, Cary, NC).

Rationale for selection of subject

Sample Size Calculation. Change in mean pulmonary artery pressure was used to estimate the sample size required to achieve satisfactory statistical power for this study. We calculated our sample size to be well-powered to detect a 15% decrease in mean mPAP (a clinically significant change). This would be approximately 4 mmHg at our minimum mPAP cut-off of 25 mmHg. We assumed a standard deviation of 5.5 derived from previous HFpEF treatment studies.¹³ Thus, with a power of 0.95, and a two-sided α of 0.05, we would require a sample size of 27 patients. Because of the length of the study, we estimate an additional 30% will be needed to offset study attrition, thus a total sample size up to 40 patients will be enrolled.

Safety Monitoring and Assessment

Patients will be called 1 week after each dose change. BP and HR will be measured at each visit, as well as BMP, ECG, and LFT will be performed as safety assessments. Accumulated safety data will be reviewed by a study physician every six months to assess overall safety of nebivolol treatment.

Data Management

Patient data will be initially recorded using the patient data collection form and RHC data collection form. Patient data will then be transferred and stored using a custom-built REDCap database. REDCap is a secure, web-based application for building and managing online databases for the collection and entry of research data. Consents and other paper documentation will be kept in a locked cabinet in [name] locked, private office.

Risks and Benefits

Patients may not directly benefit. There is a potential benefit from improvements in progression of their PH. The potential risks include:

- Nebivolol: Risk of side effects such as: large decrease in blood pressure (less likely), headache (less likely), dizziness (less likely), nausea (rare), fatigue (rare), diarrhea (rare), difficulty breathing (very rare), and slow heart rate (very rare).
- Blood draws: discomfort at needle site (less likely), bruising at needle site (less likely), pain at site (less likely), swelling of vein (rare), fainting (rare), and infection (rare).
- Echocardiogram: no risks associated with this procedure
- Right heart catheterization: pain (less likely) or infection at catheterization sight (rare), vascular/valve damage (very rare), edema (rare), bruising (less likely), internal bleeding (very rare), blood clots (very rare), excessive fluid around the heart (very rare), and irregular heart rhythms (very rare).
- 6-minute walk distance: fatigue during walk (less likely)
- Accidental disclosure of PHI (rare)

Relevant Literature

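### No symptom record is scheduled before the first nebivolol dose, so for five listed side effects the only baseline is patient recall

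*Combined protocol and SAP*

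**What the plan says.** In the schedule table under Methods, the row "adverse effect assessment X X X X" is marked at Call 1 (week 1), Call 2 (week 2, made only if needed), Call 3 (week 5) and Call 4 (week 9). It is blank at Visit 1/1A. The itemised Visit 1 and Visit 1A lists agree with the table: they contain no symptom question, and nebivolol is started at one of these two visits.

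Each call script has two symptom questions. The first is "How does patient feel compared to before starting study drug" and the second is "Any perceived side effects".

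Some baselines are recorded. The table has "dyspnea index X X X X", with marks at Visits 1 to 4. The visit lists include "Vital signs: blood pressure, pulse, respirations, height, weight, etc". EKG and chemistry are also done at Visit 1 and repeated.

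Inclusion criterion 3 requires "NYHA class II-IV symptoms". Patients on another beta-blocker stop it and begin nebivolol the same day or the next. Risks and Benefits lists a large fall in blood pressure, headache and dizziness as less likely effects of nebivolol, followed by "nausea (rare), fatigue (rare), diarrhea (rare), difficulty breathing (very rare), and slow heart rate (very rare".

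Under Safety Monitoring and Assessment, "Accumulated safety data will be reviewed by a study physician every six months to assess overall safety of nebivolol treatment". The plan gives no definition of a treatment-emergent event, no grading or attribution rule, and no adverse-event analysis.

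**The concern.** The study is open-label and describes no control arm, so a reported symptom can be judged only against the same patient's state before the drug. For several listed side effects that state is never written down. Fatigue and dizziness can come from heart failure or from the beta-blocker just stopped, as well as from nebivolol.

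Two errors become possible. A symptom the patient already had may be recorded as a nebivolol effect. A symptom that was present and then worsened may be missed or dismissed, because there is no earlier severity to set it against. Both would reach the physician's six-monthly safety review, and they may also reach the judgements about whether a dose step is tolerated. A pre-dose record cannot be recovered once a patient has started treatment.

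**Working it through.** **1. When symptoms are asked about** (schedule table, visit lists and call scripts in Methods)

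| Contact | Week | Adverse effect assessment | On nebivolol? |
|---|---|---|---|
| Visit 1/1A | 0 to 1 | no | starts here |
| Call 1 | 1 | yes | yes |
| Call 2 (if needed) | 2 | yes | yes |
| Visit 2 | 4 | no | yes |
| Call 3 | 5 | yes | yes |
| Visit 3 | 8 | no | yes |
| Call 4 | 9 | yes | yes |
| Visit 4 | 18 | no | yes |

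There are no assessments before the first dose and three or four after it. Recall of the pre-drug state spans nominally 1 week (Call 1) to 9 weeks (Call 4).

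**2. Which listed side effects have a recorded baseline** (Risks and Benefits against the Visit 1 list)

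| Listed effect | Visit 1 record |
|---|---|
| Fall in blood pressure | vital signs |
| Slow heart rate | pulse, EKG |
| Difficulty breathing | dyspnea index |
| Headache, dizziness, nausea, fatigue, diarrhea | none scheduled |

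Three of the eight listed effects have a baseline measure and five do not.

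**3. Possible size**

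The plan gives no figure on this point. Inputs:

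- N = 40 (planned enrolment, Methods).
- p = share of patients with a given symptom at entry. The documents give none; assumed 0.10, 0.30 and 0.50.
- r = share of those patients whose old symptom is recorded as a side effect. Assumed 0, 0.25, 0.50 and 1.

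With no drug effect, expected false reports for that symptom = N × p × r.

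| p | r = 0 | r = 0.25 | r = 0.50 | r = 1 |
|---|---|---|---|---|
| 0.10 | 0 | 40 × 0.10 × 0.25 = 1 | 2 | 4 |
| 0.30 | 0 | 40 × 0.30 × 0.25 = 3 | 6 | 12 |
| 0.50 | 0 | 40 × 0.50 × 0.25 = 5 | 10 | 20 |

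The column r = 0 is perfect recall. The column r = 1 means no comparison with the pre-drug state at all, which is not what the call script asks for. If only the 27 patients of the sample-size calculation are counted, every entry shrinks by 27/40; for example, 3 becomes 27 × 0.30 × 0.25 = 2.0.

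**4. Effect on the planned analyses**

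The planned sample size of 27 reproduces: a paired t-test with difference 4 mmHg, SD 5.5 and two-sided alpha 0.05 has power 0.953 at n = 27. No symptom report enters that calculation or the mPAP and PCWP comparisons.

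**The case against.** The strongest reply is that the calls already ask about change. The first question compares the patient's state with that before the drug, and the second asks about side effects, not about symptoms in general. This stands against a stronger reading that a reader might infer: that side-effect counts must rise once dosing begins even if nebivolol does nothing. That would require patients to ignore both questions, so r = 1 is a ceiling and not an expectation. It does not close the gap. The first question is global and names no symptom, and the second leaves attribution to a patient who knows what they are taking.

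A reader might also infer that the safety review cannot separate drug effects from background at all. The documents do not support that either. Dyspnea, blood pressure, pulse, EKG and laboratory values have Visit 1 values repeated later, and Calls 3 and 4 report safety results against baseline. The gap is confined to the five symptoms in step 2.

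Other replies stand in part:

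- The nine-week recall applies to Call 4 only. The scheduled dose increases are considered at weeks 2 and 4, so Call 4 informs neither.
- Exclusion 9 bars third-generation beta-blockers and high doses of others. This limits carry-over from the previous drug, but lower doses of other agents remain eligible.
- The patient data collection form is not in the documents and may hold baseline symptoms. That cannot be excluded, but the schedule does not call for it.
- The own-control statement in Statistical Methods concerns the hemodynamic t-test, and no adverse-event comparison is planned. No planned estimate is therefore biased.

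**Conclusion.** The concern holds in limited form. For headache, dizziness, nausea, fatigue and diarrhea, the plan's only baseline is unblinded recall over 1 to 9 weeks. Some pre-existing symptoms may therefore be recorded as nebivolol side effects, and worsening of an existing one is hard to document. If a quarter of old symptoms were misattributed, that would mean 1 to 5 false reports per symptom among 40 patients, within a full range of 0 to 20. Both the prevalence and the misattribution share are assumptions, because the documents give neither. For effects the protocol itself calls rare, even a few such reports could alter the tolerability picture.

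What is affected is the descriptive safety review and possibly the tolerance judgements. A reader should not infer any bias in the primary mPAP and PCWP analyses or any fault in the sample size from this point. It is a cheap improvement, best made before further patients start treatment.

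**What to change.** - Mark adverse effect assessment at Visit 1, or at Visit 1A when the drug starts there, to be completed before the first dose.
- Record presence and severity of the symptoms already named in Risks and Benefits: headache, dizziness, nausea, fatigue, diarrhea and difficulty breathing.
- Ask the same list at every later adverse effect assessment.
- In Safety Monitoring and Assessment, count a symptom as treatment-emergent only if it is new or worse than the pre-dose record, and show on-treatment counts beside pre-dose counts.

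If the data collection form already captures these symptoms before dosing, it is enough to say so in the schedule and add the definition.

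The cost is a few minutes per contact, one added form in REDCap, and a short amendment covering the checklist, the definition and the tabulation. No visit or procedure is added. The downside is that a fixed list prompts more reports than an open question, which is why the same list has to be used before and after the first dose. The change does not fill the separate interval between week 9 and week 18, where the table shows no adverse effect assessment.

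### The visit schedule omits the promised call one week after the week-2 dose increase, and it lists no side-effect question after week 9

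*Combined protocol and SAP*

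**What the plan says.** In the schedule table (Methods), the row for "adverse effect assessment" has four marks: Call 1 (week 1), Call 2 (week 2), Call 3 (week 5) and Call 4 (week 9). All four visit columns are blank. The itemised lists that follow agree with the table: the question "Any perceived side effects" stands under each phone call and under no visit.

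Methods starts patients not on a beta-blocker at 2.5 mg and those already on one at 5 mg. The two later on-study steps are:

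- Call 2, which is held only if needed: "If tolerated, increase nebivolol dose to 5 mg (after approval by study physician" is the instruction.
- Visit 2 (week 4): "If tolerated, increase nebivolol dose to 10 mg once daily".

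The table row for nebivolol dose changes is marked at Visit 1/1A, Call 2, Visit 2 and Visit 4. For Visit 4 (week 18) the text gives no specific dose step, only this: "Based on study physician recommendation, patients will be advised on how to proceed with beta-blocker treatment after the end of the study".

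The section Safety Monitoring and Assessment states, without exception: "Patients will be called 1 week after each dose change". It also names blood pressure, heart rate, metabolic panel, ECG and liver tests as safety assessments.

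**The concern.** There are two separate points.

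The first is an inconsistency between two parts of the protocol. The safety section promises a call a week after every dose change. The schedule lists one after the start of treatment and one after the week-4 step, but none after the week-2 step. The missing call would fall between two increases, where its answers would inform the second. Staff working from the table and lists would not make it.

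The second is a gap that breaks no stated rule. Listed side-effect questions stop at week 9, although treatment runs to week 18. Visit 4 ends with advice on further beta-blocker treatment, but its list does not ask how the patient has tolerated the drug.

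What is at stake is the capture of symptoms. Risks and Benefits names headache, dizziness, nausea and diarrhea among nebivolol's side effects, and the scheduled measurements would not reliably pick these up. Tolerance-based titration, the closing advice and the six-monthly review of accumulated safety data all draw on such information. The efficacy analysis is not affected.

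**Working it through.** The protocol gives no figure of its own to reproduce here. The check applies the safety section's rule to each dose change marked in the table, then looks for the resulting week among the listed calls (weeks 1, 2, 5 and 9).

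Call due = week of dose change + 1.

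| Dose change | Week | Call due | Listed? |
|---|---|---|---|
| Start (Visit 1) | 0 | 0 + 1 = 1 | Yes, Call 1 |
| 2.5 to 5 mg (Call 2) | 2 | 2 + 1 = 3 | No |
| To 10 mg (Visit 2) | 4 | 4 + 1 = 5 | Yes, Call 3 |
| Any change at Visit 4 | 18 | 18 + 1 = 19 | No |

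If Visit 1A delays the start, Call 1 may come less than a week after the first dose. That does not change the table's main result.

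*Who is affected by the week-3 gap.* Only patients who start on 2.5 mg and are increased at Call 2. Patients who start on 5 mg have no week-2 step, so the rule is met for them up to Visit 4. The documents do not give the size of the subgroup.

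*What the subgroup's schedule looks like after the week-2 increase.*

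- Next listed contact: Visit 2, 4 − 2 = 2 weeks later, with no side-effect question listed.
- Next listed side-effect question: Call 3, 5 − 2 = 3 weeks later, against the 1 week promised.
- Call 3 comes 5 − 4 = 1 week after the possible step to 10 mg. Between weeks 2 and 4, while the patient is on 5 mg, no side-effect question is listed.

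*The end of the study.* The last listed question is at week 9 and the last visit at week 18: 18 − 9 = 9 weeks, and 9/18 = 50% of the schedule. No contact is listed in between. At week 18 the list has blood samples, vital signs, dyspnea index, medication history, walk test, ECG, echocardiogram and catheterization.

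**The case against.** The strongest reply is that the schedule is not the whole of the monitoring.

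- The step to 10 mg is conditional on tolerance, and Methods keeps patients who cannot tolerate an increase on their maximum tolerated dose. Someone must therefore judge tolerance at Visit 2, in person, with vital signs, ECG, laboratory tests, dyspnea index and walk test at hand. This stands. A reader might infer that the dose is doubled with no tolerability check; the documents do not support that. They do show that Call 2 carries the same tolerance condition and still lists the side-effect question separately, whereas Visit 2 does not.
- The data collection form named under Data Management is not in the documents and may hold a side-effect field. This also stands. A reader might infer that after week 9 side effects are recorded only if patients volunteer them; that cannot be concluded without the form. The form could not, however, supply a week-3 call that is not scheduled.
- The safety rule is itself operative text, so staff who follow it would call at week 3. That is fair, and it makes the first point a mismatch within the protocol. It is no proof that the call would be missed.
- Scheduled up-titration ends at week 4, and spacing contacts out on a stable dose is defensible. In part, yes. But Call 4 also follows a visit with no scheduled dose change and still asks, so the protocol already sees a use for the question on a stable dose.
- No planned analysis has an adverse-event endpoint. True, and it limits the weight of the point.

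Nor may a reader infer that safety monitoring is absent in the second half: objective checks are scheduled at week 18, and blood pressure, heart rate and breathing are addressed by them.

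**Conclusion.** Both points hold in limited form.

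The schedule does not match the protocol's own call rule for patients started on 2.5 mg and increased at week 2. Their next listed side-effect question comes at 3 weeks instead of 1, after the next possible increase. This rests on the text alone, and confidence is high.

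Separately, no side-effect question is listed for the last 9 of 18 weeks, final visit included. That is certain for what the schedule lists. Whether symptoms go uncollected in practice is less certain, because it depends on the unseen form and on how tolerance is judged at visits.

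On a literal reading of the table, the rule also calls for a week-19 contact if the dose is changed at Visit 4. The protocol does not say whether the rule is meant to reach past the end of the study.

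This is a modest safety-schedule correction, worth making because it is specific and nearly free.

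**What to change.** 1. Add a week-3 call for patients increased at Call 2, with the two questions the other calls already use (how the patient feels compared with before study drug, and any perceived side effects). The answers are then available before the Visit 2 decision.
2. Mark the adverse-effect row at Visit 4 and add the same two questions to the Visit 4 list. Ask about the interval since Call 4, before the end-of-study beta-blocker advice.
3. Either add a call one week after any dose change made at Visit 4, or state in the safety section that the rule covers on-study dose changes only.

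The cost is one short call for a subset, a few minutes at a visit that already takes place, and an edit to the table and lists, plus a week-19 call if that option is chosen under item 3. The limitation is that the Visit 4 question relies on 9-week recall: it closes the gap in coverage but leaves 9 weeks between questions. Only a contact between weeks 9 and 18 would shorten that, and the sponsor could add one if recall is a worry.
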